LIFITEGRAST 5% FOR THE TREATMENT OF DRY EYE IN HABITUAL SOFT CONTACT LENS WEARERS

Principal Investigator: [name], OD, FAAO Version Number: v.5.0

03AUG2021

V5.0 PROTOCOL CHANGE SUMMARY				
Control Treatment	Changed from single use vials of Systane Original Preservative Free artificial tears to lifitegrast vehicle.			
Randomization and Masking	Changed to explain labeling on lifitegrast vs vehicle.			
Minor Formatting Changes	Minor changes for clarification.			
V4.0 PROTOCOL CHANGE SUMMARY				
Adverse Events	Edited to add detail to adverse events section.			
V3.0 PROTOCOL CHANGE SUMMARY				
Sponsor	Clarified that Novartis is not the sponsor of the study, but rather providing drug and budget.			
Study Duration	Clarified Study Timeline			
Control Treatment	Changed from lifitegrast vehicle to single use vials			
Overall Design	of Systane Original Preservative Free artificial tears. Added language to require subjects who are currently using reusable contact lenses to use Clear Care solution to clean and disinfect the lenses.			
Eligibility Criteria	Added Inclusion 10: Subjects currently wearing reusable contact lenses must be willing to use Clear Care solution for cleaning and disinfecting throughout the study. Added Exclusion 11: Punctal plug insertion in the last 3 months, or presence of punctal plugs at the time of the exam.			
Randomization	Edited to include information regarding updated randomization method.			
Sample Size Justification	Updated sample size justification			
Statistics	Updated statistical methods.			
Grammatical /Formatting Edits	Minor grammatical/ formatting changes to clarify content.			
V2.0 PROTOCOL CHANGE SUMMARY	content.			
Sponsor	Changed from Shire Human Genetic Therapies, Inc. to Novartis Pharmaceuticals Corporation.			
Control Treatment	Changed from single use vials of preservative free artificial tears to lifitegrast vehicle.			
Masking	Changed wording from "branding" to "any labeling" in relation to how masking will be maintained.			
Study Procedures	Added Monocular High Contrast, High Luminance Visual Acuity to each visit.			
Inclusion Criteria	Clarified Inclusion 9 to specify that entrance Snellen visual acuity will be utilized to determine subject eligibility.			

STATEMENT OF COMPLIANCE

This clinical trial will be conducted in accordance with the principles of The Declaration of Helsinki, and will follow GCP guidelines. The protocol, informed consent form(s), recruitment materials, and all participant materials will be submitted to the IRB for review and approval. Any amendment to the protocol will require review and approval by the IRB before the changes are implemented to the study. The study will be registered on clinicaltrials.gov.

1 PROTOCOL SUMM	1ARY	
1.1 SYNOPSIS		
Title:	Lifitegrast 5% for the Treatment of Dry Eye in Habitual Soft Contact Lens Wearers	
Principal Investigator:	[name], OD	
Study Drug/ Budget Provided by:	Novartis Pharmaceuticals Corporation	
Description of Study Intervention:	This is a prospective, single site, randomized, double masked, comparator-controlled study designed to evaluate the efficacy of lifitegrast ophthalmic solution 5% in treating the symptoms of dry eye in soft contact lens (CL) wearers as compared to control. We hypothesize that there will be a significant improvement in dry eye symptoms in contact lens wearers using lifitegrast as compared to those being treated with control (lifitegrast vehicle).	
Objectives:	Primary Outcome: To determine the efficacy of lifitegrast ophthalmic solution 5% in treating the symptoms of dry eye in contact lens wearers as measured by change in total score on the Contact Lens Dry Eye Questionnaire-8 (CLDEQ-8) after 8 weeks of treatment. Secondary and Exploratory Outcomes: a. Change in tear osmolarity at 8 weeks in the lifitegrast 5% group compared to the control b. Forced choice questionnaire at week 8 asking if the participant felt that their symptoms improved to the point that they would continue treatment outside of the study c. Change in total score on the CLDEQ- 8 at 2 weeks and 4 weeks d. Trends in responses to individual questions	
Estimated duration from FPFV to Study Report:	14 months	
Participant Duration:	Visit 1: Day 0 (Baseline Visit) Visit 2: Week 2 Visit 3: Week 4 Visit 4: Week 8	

2 STUDY DESIGN

2.1 STUDY RATIONALE

Dry eye disease (DED) is commonly encountered as part of clinical practice. It has been estimated that more than 16 million adults in the United States have diagnosed DED.¹ DED is defined as "a multifactorial disease of the ocular surface characterized by loss of homeostasis of the tear film, and accompanied by ocular symptoms, in which tear film instability and hyperosmolarity, ocular surface inflammation and damage, and neurosensory abnormalities play etiological roles."² DED can be associated with or induced by the use of contact lenses.² Changes to the tear film in contact lens (CL) wearers with dry eye include a thinner lipid layer, tear film instability, lower basal tear turnover rate and decreased tear meniscus volume.²

Lifitegrast ophthalmic solution 5% is an anti-inflammatory drug approved to treat both the signs and symptoms of DED. It acts as a lymphocyte function associated antigen-1 antagonist (LFA-1). This allows for inhibition of T-cell adhesion, migration and proliferation.³ This study will seek to determine if using lifitegrast ophthalmic solution 5% will help improve dry eye symptoms in subjects who are existing habitual soft CL wearers as compared to control (lifitegrast vehicle).

The Contact Lens Dry Eye Questionnaire-8 (CLDEQ-8) will be utilized to establish baseline symptoms and to monitor for changes with treatment. This questionnaire has been validated to reflect subject opinion of soft CLs in clinical trials.⁴ A score of greater than or equal to 12 has be shown to identify soft CL wearers who would benefit from management of their CL related symptoms, with a change of 3 identifying a clinically important difference on the CLDEQ-8 total score.⁵ For this study, subjects must have a score of 12 or greater on at baseline in order to be eligible for participation.

2.2 OVERALL DESIGN

This is a prospective, single site, randomized, double masked, comparator-controlled study designed to evaluate the efficacy of lifitegrast ophthalmic solution 5% in treating the symptoms of dry eye in soft contact lens wearers as compared to control. We hypothesize that there will be a significant improvement in dry eye symptoms in contact lens wearers using lifitegrast 5% as compared to those being treated with control (lifitegrast vehicle).

Potential study candidates will sign an informed consent form prior to any clinical procedures or tests specific to the protocol are performed. All screening examination procedures will be performed by the investigator or trained personnel working under the investigator's supervision. Subjects will undergo examination to determine eligibility at the Baseline visit. A complete medical, ocular and medication history will be obtained. Subjects who elect to participate will complete the study as outlined in Section 2.4. Signs and symptoms will be evaluated at baseline, 2 weeks, 4 weeks and 8 weeks. All tests and measurements will be obtained in accordance with the procedures specified in this protocol.

If found to be eligible, subjects will be randomized in a 1:1 ratio to either the test product (lifitegrast 5%) or control (lifitegrast vehicle) arm. Subjects will be instructed to use the drops twice a day in each eye. Drops are to be instilled in the morning at least 15 minutes before CL insertion, and after CL removal in the evening.

Subjects who are currently using reusable contact lenses will be required to use Clear Care solution to clean and disinfect their lenses.

Subjects will be asked to return to each visit with all of the used and unused vials dispensed at the prior visit. Subject accountability will be assessed at each follow up visit by comparing the amount of used vials to the amount of expected days of use. Trends in compliance will be considered during analysis of study data.

2.2.1 OUTCOME MEASURES

The primary outcome measure is the efficacy of liftiegrast ophthalmic solution 5% in treating the symptoms of dry eye in contact lens wearers as measured by change in total score on the CLDEQ-8 after 8 weeks of treatment.

Secondary and exploratory outcomes include:

- a. Change in tear osmolarity (measured via Tear Lab) at 8 weeks in the lifitegrast 5% group compared to the control
- b. Forced choice questionnaire at week 8 asking if the participant felt that their symptoms improved to the point that they would continue treatment outside of the study
- c. Change in total score on the CLDEQ-8 at 2 weeks and 4 weeks
- d. Trends in responses to individual questions

2.3 RANDOMIZATION AND MASKING

The randomization schedule will be generated by a biostatistician using simple random sampling. Participants will be randomized within center at the first visit. After all baseline assessments are completed, the delegated unmasked study coordinator will refer to the randomization scheme to assign each subject to one of the two study arms. All study participants who are randomized into the study will comprise the intent-to-treat population. Participants will be randomized into 1 of 2 different treatment arms.

The labeling differences between the lifitegrast and the vehicle will be known to only the unmasked coordinator. The unmasked coordinator will dispense the appropriate treatment to the subject. All drug dispensing and accountability will be done by an unmasked study coordinator so the investigator can remain masked.

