3.3 SAMPLE SIZE JUSTIFICATION

Assuming normality, we calculated the statistical power for various detectable effect sizes using unpaired t-test in a two-sided hypothesis test with a significance level, 0.05, where the ratio of sample size of 1:1 is assumed between study arms. **Table 1** shows that our sample size will have adequate power to detect listed effect size. For example, we will achieve 84% power to detect a standardized mean difference of 1.12 between two groups of a size of 15 for each, which corresponds to a difference of score change by 3 with standard deviations 3.2 and 2.0 for each group⁵. Up to 40 subjects will be enrolled with the goal of randomizing 30 subjects (15 per arm). This will allow for a 25% screen-failure rate. Note that for each

domain score and the overall score, the power is the same for each effect size since they are standardized, but the mean change corresponding to a given effect size differs.

Table 1

Sample size (N)	Unpaired t-test		
N1 vs. n2	Effect size 1	Power (%)	
15 vs. 15	1	75.3	
	1.12	84.4	
	1.2	87.5	

¹ standardized mean difference of 2 groups

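### Section 2.3 describes nothing that holds the arms near 15/15, and uneven arms would distort a pooled t-test under the plan's own unequal SDs; the loss of average power is small

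*Combined protocol and SAP*

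**What the plan says.** Section 2.3 gives the allocation method in one sentence: "The randomization schedule will be generated by a biostatistician using simple random sampling". It adds "Participants will be randomized within center at the first visit", but this is a single-site study, so that restricts nothing. The protocol mentions no block size, stratification factor or rule that forces final balance.

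Other sections depend on balance. Section 2.2 says "subjects will be randomized in a 1:1 ratio to either the test product (lifitegrast 5%) or control (lifitegrast vehicle) arm". Section 3.3 bases its power on the t-test "where the ratio of sample size of 1:1 is assumed between study arms", and concludes that "we will achieve 84% power to detect a standardized mean difference of 1.12 between two groups of a size of 15 for each". It ties the effect size to a difference of 3 points with SDs of 3.2 and 2.0, without saying which arm has which SD. It describes 30 randomised participants, 15 per arm, as a goal.

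Section 5 names t-tests for the primary outcome, with a Wilcoxon test as the alternative for non-normal data. It does not say whether the t-test is pooled or Welch.

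**The concern.** Every row of Table 1 is computed at 15 versus 15, but nothing in Section 2.3 secures that split. Simple randomisation fixes arm sizes only in expectation, and with 30 participants the realised sizes can be well apart.

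This matters mainly because the plan expects unequal SDs. A pooled t-test is close to its nominal level with equal arms even when the SDs differ. With unequal arms it is not. It rejects too often if the more variable arm is the smaller, and too seldom if it is the larger. The level of the primary test would then depend on an accident of the schedule.

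**Working it through.** **Inputs.** From Section 3.3: 30 randomised, 15 per arm; two-sided alpha 0.05; unpaired t-test; difference 3; SDs 3.2 and 2.0. From Section 2.3: the allocation method.

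**1. The plan's own figure.** The root-mean-square SD is √((3.2² + 2.0²)/2) = √7.12 = 2.668, so d = 3/2.668 = 1.124. Two-sided noncentral-t power, with df = n1 + n2 − 2 and noncentrality d√(n1·n2/(n1 + n2)), is 84.4% at 15/15. That matches Table 1. Rounding d to 1.12 gives 84.1%. A Welch test at 15/15 gives 83.9%.

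**2. Arm sizes under independent 50:50 assignment,** Binomial(30, 0.5):

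| Split | Probability |
|---|---|
| exactly 15/15 | 14.4% |
| 12/18 or more uneven | 36.2% |
| 11/19 or more uneven | 20.0% |
| 10/20 or more uneven | 9.9% |

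**3. Arm sizes if 15 of 30 slots are drawn.** The split is exact if all 30 slots are used. If only m are used, P(k in one arm) = C(15, k)·C(15, m − k)/C(30, m). The documents give no figure for a shortfall, so m is an assumption. With m = 28 the split is 14/14 (52%) or 13/15 (48%). With m = 24 it is 12/12 in 35% of cases and 10/14 or worse in 17%.

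**4. Power under independent assignment.** Pooled-t power at d = 1.12 is 84.1% at 15/15, 82.7% at 12/18, 81.4% at 11/19 and 79.7% at 10/20. Averaged over all splits it is 82.8%. At d = 1.124 the average is 83.1%, against 84.4% at 15/15. The loss is about 1.3 points either way.

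**5. Type I error of a pooled t-test, SDs 3.2 and 2.0.** The true variance of the difference is 3.2²/n1 + 2.0²/n2. The pooled formula expects [(n1 − 1)3.2² + (n2 − 1)2.0²]/28 × (1/n1 + 1/n2).

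- SD-3.2 arm 12, other arm 18: true 0.853 + 0.222 = 1.076; pooled 6.451 × 0.1389 = 0.896. The test statistic is inflated by √(1.076/0.896) = 1.096. The critical value 2.048 then acts like 2.048/1.096 = 1.87, a two-sided level of about 7.2% on 28 df.
- SD-3.2 arm 18, other arm 12: true 0.902; pooled 1.082; factor 0.913; level about 3.3%.

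Simulation with normal data confirms this approximation:

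| Split | SD-3.2 arm smaller | SD-3.2 arm larger |
|---|---|---|
| 15/15 | 4.9% | same |
| 12/18 | 7.3% | 3.5% |
| 10/20 | 9.1% | 2.6% |

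Repeat runs agree to a few tenths of a point.

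**6. Welch test.** It holds about 5% throughout. Its power is 77.7% at 12/18 with the SD-3.2 arm smaller and 86.2% with it larger. At 10/20 the two figures are 70.6% and 85.7%.

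**7. Permuted blocks.** With blocks of 2 and 4, enrolment of 30 can stop at worst halfway through a block of 4, at 2 to 0. The final split is therefore 15/15 or 14/16. The arithmetic of step 5 gives a pooled-t level of about 5.7% or 4.4% at 14/16.

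**The case against.** **Power is hardly affected.** A reader might infer from the 14.4% chance of an exact 15/15 split that the stated 84% power is unlikely to be met. The documents' own inputs do not support that. Splits of 14/16 and 13/17 cost almost nothing, power at d = 1.12 falls below 80% only at 10/20 or worse, and the average loss is 1.3 points. Nor do uneven arms always lower power: under Welch, the favourable direction beats 15/15. Quoting only the 71% at 10/20 would hide the equally likely mirror case at about 86%. This objection stands.

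**The phrase is ambiguous.** Drawing 15 of 30 slots fits Sections 2.2 and 3.3 and gives exact balance at full recruitment. This also stands, so the imbalance is conditional on the reading. But a phrase with two materially different meanings needs to be settled, and the slot reading loses its guarantee if fewer than 30 are randomised.

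**Inflation and deflation are equally likely.** At 12/18 the two directions average (7.3 + 3.5)/2 = 5.4%, and at 10/20 (9.1 + 2.6)/2 = 5.85%. So the error rate over all possible schedules is only slightly raised. That is fair, but only one schedule will be used, and its split will be known.

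**Naming Welch would protect the level.** True, and it would be sensible. It would still leave power dependent on which arm turned out smaller.

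**Covariate balance.** A reader might also blame simple randomisation for imbalance in lens type. That does not support blocking: such imbalance arises even at 15/15, and unstratified blocks leave it essentially unchanged. Section 5 also plans to examine balance in lens modality and to adjust for characteristics that differ.

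**Conclusion.** The point holds as a cheap improvement to the design. It is not a defect that undermines the stated power; unrestricted randomisation is a valid method.

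Under independent assignment there is a 36.2% chance of 12/18 or worse, so about 18% in each direction. At 12/18 the pooled-t level would be about 7.3% or 3.5% instead of 5%; at 10/20, about 9.1% or 2.6%.

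These figures rest on four assumptions: that the phrase means independent 50:50 assignment; that 30 are randomised and analysed; that the change scores are normal with the SDs in Section 3.3; and that the t-test is pooled. The last is not stated, although the pooled formula is the one that reproduces the 84.4% in Table 1. If the SDs are in fact equal, the effect on type I error disappears and only the small power loss remains.

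**What to change.** In Section 2.3, replace simple random sampling with permuted-block 1:1 randomisation using small, randomly varying block sizes (for example 2 and 4) withheld from masked staff. This secures 15/15 or 14/16 at 30 participants and limits imbalance if recruitment stops early.

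The cost is one sentence and a new schedule from the same biostatistician. The downside is slight predictability near the end of a block. Varying the sizes limits this, and Section 2.3 already confines dispensing and accountability to an unmasked coordinator.

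Stratifying by lens type is a separate, optional choice. It should be argued on its own merits, not as part of this change.

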2.4 STUDY PROCEDURES

Procedures	Visit 1 (Baseline)	Visit 2 (2 weeks ±3 days)	Visit 3 (4 weeks±5 days)	Visit 4 (8 weeks ±5days)
Informed consent	Х			
Medical/ Ocular History (including artificial tear/ rewetting drop use, habitual contact lens information and typical wearing time, concomitant medications and allergies) ^a	X	Х	Х	Х
Drug Accountability ^b		Χ	Χ	Χ
Entering Acuity (Snellen) ^c	Х	Χ	Χ	Χ
LogMAR Visual Acuity, High Contrast, High Luminance, OD and OS	Χ	Χ	Χ	Χ
CLDEQ-8 Administration	X	Χ	Χ	Χ
Tear Osmolarity ^d	Х			Χ
Habitual Contact Lens Fit Assessment ^e	Х	Χ	Χ	Χ
Removal of Contact Lenses	Х	Χ	Χ	Χ
Slit lamp Biomicroscopy ^f	Χ	Χ	Χ	Χ
Corneal Staining Assessment (NaFI) ^g	Χ	Χ	Χ	Χ
Tear Break Up Time (TBUT) in seconds ^h	Χ	Χ	Χ	Χ
Lissamine Green Staining ⁱ	Χ	Χ	Χ	Χ
Schirmer Testing ^j	Χ	Χ	Χ	Χ
Randomization	Х			
Drug Dispensing	Χ	Χ	Χ	
Forced Choice Questionnaire ^k				Χ
Contact Lens Re-Insertion (with irrigation if necessary)	Х	Χ	Χ	Χ
Exit Acuity (Snellen)	Χ	Χ	Χ	Χ
Adverse Events	Χ	Χ	Χ	Χ

- a. Artificial Tear (AT)/ Rewetting drop use will include date of last use and average use per week.
- b. Amount of vials used will be compared to amount of expected vials used based on number of days since the subject's last visit.
- c. Subjects are to report to each visit wearing their habitual lenses. Acuity will be recorded as the last line in which the subject was able to read at least half of the letters. Plus and minus notation will be used to indicate additional letters read beyond the recorded acuity line or missed on the recorded acuity line.
- d. TearLab will be used per manufacturer's guidelines to measure tear osmolarity. This procedure must be performed prior to any drops being instilled in the eye for at least 2 hours prior.
- e. Lenses must have an adequate fit (centration, limbal/corneal exposure and movement) as determined by the investigator. Lens wettability and deposits will also be assessed.
- f. Slit lamp grading scale will be based on: Efron Grading Scale⁶
- g. Grading scale: NEI/Industry Grading System⁷
- h. TBUT will be recorded in number of seconds 0-15 or greater than 15 seconds
- i. Grading scale: NEI/ Industry Grading System⁷
- j. Schirmer testing will be performed without anesthesia for 5 minutes in each eye.
- k. The questionnaire will ask the subject if he/she felt their symptoms improved to the point that he/she would continue outside the study.

2.5 RISK/BENEFIT ASSESSMENT

2.5.1 KNOWN POTENTIAL RISKS

Lifitegrast ophthalmic solution 5% will be dispensed to subjects in the test arm and will be used for 8 weeks.

The common (5-25%) risks associated with lifitegrast 5% are8:

- Instillation site irritation
- Dysguesia
- Reduced Visual Acuity

Less common (1-5%) side effects include⁸:

- Blurred vision
- Conjunctival hyperemia
- Eye irritation
- Headache
- Increased lacrimation
- Eye discharge
- Eye discomfort
- Eye pruritis
- Sinusitis

As with any medication, allergic reactions are possible. A serious, potentially life-threatening allergic reaction known as anaphylaxis is possible.

Subjects will be required to wear their habitual contact lenses throughout the study. The most common risks associated with CL wear include:

- Burning, stinging, tearing, redness and/or itching of the eyes
- Contact lens related ocular discomfort
- Foreign body sensation
- Dryness

More serious side effects of CL wear are less common, and include:

- Corneal infiltrates, ulcers or erosions
- Corneal edema
- Corneal neovascularization
- Iritis

2.5.2 KNOWN POTENTIAL BENEFITS

Subjects may experience an improvement in signs and symptoms of dry eye if they are in the treatment arm. They might not experience any benefits if they are in the control arm. The efficacy of lifitegrast in contact lens wearers is not known.

2.5.3 ADVERSE EVENTS

An adverse event (AE) is "any untoward occurrence (physical, psychological, social, or economic) in a human subject participating in research". The event is not necessarily unexpected. The event may have

been described in the informed consent as a risk of the study. Adverse events include abnormal laboratory findings, a symptom, or disease temporally associated with the use of an investigational agent, or the progression of disease, whether or not related to the investigational product.

Anticipated Adverse Events: Anticipated adverse events include those listed in the Known Potential Risks section, informed consent documents, the lifitegrast package insert and/or those known to be associated with contact lens wear or dry eye.

Anticipated adverse events will be recorded in the appropriate source documents and case report forms. At a minimum, the following data will be collected:

- Description of the event
- Onset
- Location
- Seriousness
- Relation to study drug
- Expectedness
- Actions taken
- Follow up
- Resolution date and outcome

Serious Adverse Event (SAE): Serious adverse events are any untoward medical occurrences such as death, significant disability/incapacity, In-patient hospitalization or prolongation of existing hospitalization or congenital anomaly/birth defect.

Unexpected Adverse Effect (UAE): An unanticipated problem involving risk to human participants or others is one that was unforeseen at the time of its occurrence and indicates that participants or others are at an increased risk of harm. Unexpected adverse events are those that are not already described as potential risks in in the Known Potential Risks section, informed consent documents, the lifitegrast package insert and/or those known to be associated with contact lens wear or dry eye or not part of an underlying disease.

SAE/UAE Reporting

An event is considered reportable if it is unexpected or serious. Once an event is **s**uspected by the investigator as reportable, the PI shall be consulted to determine how the event should be reported. When the event is determined to be reportable by the PI, the Novartis shall be contacted immediately (within 24 hours) by e-mail or phone. A written report will then be submitted to the sponsor and the IRB as soon as possible, but no later than 5 working days after discovery of the event (or sooner, as specified by the sponsor or IRB).

• The PI will report (within 24 hours) the SAE/UAE to the IRB and Novartis as per the "Safety Data Collection and Reporting Responsibilities" agreement with Novartis. This information will be reported as soon as it becomes available.

- The PI will also report any drug exposure during pregnancy and any instances of drug misuse or abuse to Novartis.
- At a minimum, the following will be reported: the person who reported the event, information
 about the patient, details of the study drug, and details on the safety events experienced by the
 patient.
- The PI or designee shall submit a SAE/UAE Initial Report to the IRB.
- For suspected unexpected SAEs (SUSARs), safety reports such as Investigator Notifications or SUSAR listings will be prepared as per the "Safety Data Collection and Reporting Responsibilities" agreement with Novartis.

SAE/UAE Follow-up

Follow up reports shall be made to Novartis and the IRB until resolution of the event.

- The SAE (or AE) follow-up information shall be submitted following the "Safety Data Collection and Reporting Responsibilities" agreement with Novartis.
- A Follow-up Report shall be submitted to the IRB as required.

The source documents must indicate:

- The event being followed
- The current status of the event
- What treatment was provided
- Any follow-up action taken/recommended
- The outcome of the event

Unmasking of Investigators and Subjects

Unmasking will be performed on an as needing basis, such as in the following scenarios:

- Serious adverse event, where unmasking is relevant to either subject care or reporting
- Drug/device recall
- Potential safety or risk management concern
- The Investigator deems knowledge of the treatment group to be essential to subject care or safety

